3.6.2. Outliers

Outliers will be identified during the data management and data analysis process, but no sensitivity analyses will be conducted. All data will be included in the data analysis.

3.7. Data Handling Conventions and Transformations

The following conventions will be used for the imputation of date of birth when it is partially missing or not collected:

- If only month and year of birth is collected, then “01” will be imputed as the day of birth
- If only year of birth is collected, then “01 July” will be imputed as the day and month of birth
- If year of birth is missing, then date of birth will not be imputed

In general, age (in years) collected at Day 1 will be used for analyses and presented in listings. If age at Day 1 is not available for a subject, then age derived based on date of birth and the Day 1 visit date will be used instead. If an enrolled subject was not dosed with any study drug, the randomization date will be used instead of the Day 1 visit date. For screen failures, the date the first informed consent was signed will be used for the age derivation. If only the birth year is collected on the CRF, “01 July” will be used for the unknown birth day and month for the purpose of age calculation. If only birth year and month are collected, “01” will be used for the unknown birth day.

The data that are continuous in nature but are less than the lower limit of quantitation (LOQ) or above the upper LOQ will be imputed as follows:

- A value that is 1 unit less than the LOQ will be used to calculate descriptive statistics if the datum is reported in the form of “ $< x$ ” (where x is considered the LOQ). For example, if the values are reported as < 50 and < 5.0 , values of 49 and 4.9, respectively, will be used to calculate summary statistics. An exception to this rule is any value reported as < 1 or < 0.1 , etc. For values reported as < 1 or < 0.1 , a value of 0.9 or 0.09, respectively, will be used to calculate summary statistics.
- A value that is 1 unit above the LOQ will be used to calculate descriptive statistics if the datum is reported in the form of “ $> x$ ” (where x is considered the LOQ). Values with decimal points will follow the same logic as above.
- The LOQ will be used to calculate descriptive statistics if the datum is reported in the form of “ $\leq x$ ” or “ $\geq x$ ” (where x is considered the LOQ).

3.8. Analysis Visit Windows

3.8.1. Definition of Study Day

Study day will be calculated from the first dosing date of study drug and derived as follows:

- For postdose study days: Assessment Date – First Dosing Date + 1
- For days prior to the first dose: Assessment Date – First Dosing Date

Therefore, study Day 1 is the day of first dose of study drug administration.

The study day for treatment period 2 (From Week 16 to Week 32) / period 3 (from Week 32 to study end) will be calculated as: Assessment Date – Date of the first dose of the corresponding treatment period (Day 1 for treatment period 1; Week 16 for treatment period 2 and Week 32 for treatment period 3) + 1. The dates of the first dose of the study drug dispensed at Day 1/Week 16/Week 32 are recorded on CRF.

3.8.2. Analysis Visit Windows

The target study days for analysis visits are provided in the [Table 3-1](#)

Table 3-1. Target Days for Analysis Visits

Nominal Visit	Study Day from Day 1/ From Week 16/From Week 32
Screening	<1
Baseline	<=1
Week 1	8
Week 2	15
Week 4	29
Week 8	57
Week 12	85
Week 16	113/1
Week 18	127/15
Week 20	141/29
Week 24	169/57
Week 28	197/85
Week 32	225/113/1
Week 36	253/141/29
Week 40	281/169/57
Week 44	309/197/85
Week 48	337/225/113
Week 52	365/253/141
Follow-up Visit	NA

The nominal visit as recorded on the CRF will be used when data are summarized by visit. Any data relating to unscheduled visits will not be assigned to a particular visit or time point. However, the following exceptions will be made:

- An unscheduled visit prior to the first dosing of study drug may be included in the calculation of the baseline value, if applicable.
- Unscheduled visits after the first dose of study drug will be included in determining the maximum postbaseline toxicity grade in safety analyses.
- The early termination (ET) data will be presented as a separate visit and labeled “ET Visit”.
- Data collected at a follow-up visit will be summarized as a separate visit and labeled “Follow-up Visit.”
- Data obtained after the follow-up visit or last dose date plus 30 days (whichever is later) will be excluded from the summaries, but will be included in the listings.

3.8.3. Selection of Data in the Event of Multiple Records in an Analysis Visit Window

Depending on the statistical analysis method, single values may be required for each analysis window. For example, change from baseline by visit usually requires a single value.

If multiple valid, nonmissing, continuous measurements are recorded for the same visit, records will be chosen based on the following rules if a single value is needed:

- In general, the baseline value will be the last nonmissing value on or prior to the first dosing date of study drug (Study Day 1), except for the analyses of active treatment period where the first dosing date of the active drug will be used. If multiple measurements occur on the same day, the last nonmissing value on or prior to the date of first dosing of study drug will be considered as the baseline value. If time is available, then use date and time to select the records with the latest time for the date. When times of these multiple measurements are not available, the average of these measurements (for continuous data) will be considered as the baseline value.
- For postbaseline values:

The record closest to the target day for that visit will be selected.

If there are 2 records that are equidistant from the nominal day, the later record will be selected.

If there is more than 1 record on the selected day and time is not collected then the average will be taken, unless otherwise specified.

If multiple valid, nonmissing, categorical measurements exist for the same visit, records will be chosen based on the following rules if a single value is needed:

- For baseline, the last available record on or prior to the date of the first dose of study drug will be selected. If there are multiple records with the same time or no time recorded on the same day, the value with the lowest severity will be selected (eg, normal will be selected over abnormal for safety electrocardiogram [ECG] findings).

- For postbaseline values:

The record closest to the target day for that visit will be selected

If there are 2 records that are equidistant from the target day, the later record will be selected

If there are multiple records with the same time or no time recorded on the same day, the value with the worst severity within the window will be selected (eg, abnormal will be selected over normal for safety ECG findings)

All records will be listed by collection date.

4. SUBJECT DISPOSITION

4.1. Subject Enrollment and Disposition

A summary of subject enrollment will be provided by treatment group and overall. The summary will present the number and percentage of subjects enrolled. For each column, the denominator for the percentage calculation will be the total number of subjects analyzed for that column.

The randomization schedule used for the study will be provided as an appendix to the CSR.

A summary of subject disposition will be provided by treatment group for both the entire study duration and by treatment phase. This summary will present the number of subjects in each of the categories listed below:

- Subjects screened
- Subjects randomized
- Safety Analysis Set
- Completed study
- Prematurely discontinued study with reasons for discontinuation
- Completed study drug
- Prematurely discontinued study drug with reasons for discontinuation

The study and drug disposition will also be presented by treatment period with the following categories:

- Completed study up to Week 16, Week 32, and through the end of the study
- Completed study drug up to Week 16, Week 32, and through the end of study
- Did not complete the study/study drug up to Week 16, Week 32, and through the end of study with reasons for premature discontinuation of the study/study drug
- Treatment switched at Week 16/Week 32

For the status of study drug and study completion, and reasons for discontinuation, the number and percentage of subjects in each category will be provided. The denominator for the percentage calculation will be the total number of subjects in the Safety Analysis Set corresponding to that column.

4.2. Extent of Study Drug Exposure and Adherence

Extent of exposure to study drug will be examined by assessing the total duration of exposure to study drug and the level of adherence relative to the study drug specified in the protocol.

4.2.1. Duration of Exposure to Study Drug

Total duration of exposure to study drug will be defined as last dosing date of any study drug minus first dosing date plus 1, regardless of any temporary interruptions in study drug administration, and will be expressed in weeks using up to 1 decimal place (eg, 4.5 weeks).

For subjects with a partial last dosing date (ie, month and year of last dose are known), the latest of the dispensing dates of study drug bottles, and the imputed last dose date [day imputed as last day of the month] will be used as the final imputed last dose date.

If only year is recorded (ie, month and day of last dose are missing) or the entire date is missing then the latest of the dispensing month of study drug bottles, study drug start month, and study drug bottle return month will be used to impute the unknown last dose month (and a year if the entire date is missing). With the month imputed, the aforementioned method will be used to impute the last dose date. If the imputed date is after the date of death, choose the death date.

The total duration of exposure to study drug will be summarized using descriptive statistics and categorical summary (number and percentage of subjects exposed). Summaries will be provided by treatment group for the Safety Analysis Set. No formal statistical testing is planned.

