3.1.3. Safety Analysis Set

The Safety Analysis Set includes all subjects who took at least 1 dose of study drug. This is the primary analysis set for safety analyses. All data collected during treatment plus 30 days after the last dose of any study drug will be included in the safety summaries.

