3.6. Missing Data and Outliers

3.6.1. Missing Data

In general, missing data will not be imputed unless methods for handling missing data are specified. Exceptions are presented in this document.

For missing last dosing date of study drug, imputation rules are described in Section 4.2.1. The handling of missing or incomplete dates for AE onset is described in Section 7.1.5.2.

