7.1.5.2. Incomplete Dates

If the onset date of the AE is incomplete and the AE stop date is not prior to the first dosing date of study drug, then the month and year (or year alone if month is not recorded) of onset determine whether an AE is treatment emergent. The event is considered treatment emergent if both of the following 2 criteria are met:

- The AE onset is the same as or after the month and year (or year) of the first dosing date of study drug, and
- The AE onset date is the same as or before the month and year (or year) of the date corresponding to 30 days after the date of the last dose of study drug

An AE with completely missing onset and stop dates, or with the onset date missing and a stop date later than the first dosing date of study drug, will be considered to be treatment emergent. In addition, an AE with the onset date missing and incomplete stop date with the same or later month and year (or year alone if month is not recorded) as the first dosing date of study drug will be considered treatment emergent.

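### The SAP's rule for incomplete last-dose dates runs to month end with death as its only upper limit, so the imputed last dose can fall after the last bottle is back at the site or the subject has left the study

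*SAP*

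**What the plan says.** SAP Section 3.6.1 sends the reader to one place: "For missing last dosing date of study drug, imputation rules are described in Section 4.2.1". Section 4.2.1 then has two cases.

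- Month and year known: the last dose is "the latest of the dispensing dates of study drug bottles, and the imputed last dose date [day imputed as last day of the month", whichever is later.
- Only the year known, or nothing known: the month is "the latest of the dispensing month of study drug bottles, study drug start month, and study drug bottle return month", and the month-end step is then applied. This paragraph closes with the only upper limit in the section: "If the imputed date is after the date of death, choose the death date".

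The imputed date is used in several places:

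- exposure, defined in SAP 4.2.1 as "last dosing date of any study drug minus first dosing date plus 1";
- the safety data window in SAP 3.1.3: "All data collected during treatment plus 30 days after the last dose of any study drug will be included in the safety summaries";
- the cut-off for by-visit summaries in SAP 3.8.2, which is the later of follow-up and last dose plus 30 days;
- AEs with an incomplete onset date, which SAP 7.1.5.2 compares by month and year with "the date corresponding to 30 days after the date of the last dose of study drug";
- the treatment-emergent laboratory window in SAP 7.2.2.1.

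Protocol Section 8.6.1 defines exposure but gives no imputation rule and no further limit.

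**The concern.** The SAP recognises that a last dose cannot follow death, but does not apply the same logic to the other events that end dosing. The month of bottle return can push the date later, yet the day of return never limits it. A subject can therefore be recorded as dosed after the last bottle was handed back, or after an early termination visit.

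The bounding dates are available. Protocol Section 5.5 requires all dispensed drug to come back and the return date to be recorded. Protocol Section 9.1.5 requires source records of dispensing, return and study completion dates. Drug accountability is scheduled at on-treatment visits from Week 1 and at early termination.

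At stake are the accuracy of reported exposure and the length of the windows that decide which safety data are counted. A wider safety window can be defended as cautious. Overstated exposure cannot be defended that way.

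**Working it through.** The plan states no figure to reproduce, so the check applies the SAP 4.2.1 rule to possible dates. Assumption, not in the documents: the true last-dose day is equally likely to be any calendar day of 2018–2019.

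**Month known.** Excess = days in month − true day.

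- Range: 0 (last day of a month) to 31 − 1 = 30 days.
- Mean in a 31-day month: (0 + 1 + … + 30)/31 = 15 days.
- Mean over a 365-day year: (7 × 465 + 4 × 435 + 378)/365 = 5373/365 = 14.7 days.

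The share of dates for which the imputed last dose falls after bottle return or study exit depends on the lag from the true last dose to that event:

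| Lag (days) | Share imputed after the event |
|---|---|
| 1 | 341/365 = 93% |
| 7 | 269/365 = 74% |
| 14 | 185/365 = 51% |
| 23 | 77/365 = 21% |
| 28 | 18/365 = 5% |
| 33 | 0% |

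The last three rows span the follow-up visit window (4 weeks ± 5 days). The problem is therefore mainly one of early bottle return, or exit at early termination without follow-up.

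**Month missing, return month governs.** Excess = return lag + (days in return month − return day), so the maximum is lag + 30: 37 days for a 7-day lag and 58 days for a 28-day lag. Example: true last dose 1 February 2019, bottle returned 1 March 2019, imputed last dose 31 March 2019, which is 58 days late. A lag of this size needs no missed visit, because many on-treatment visits are four weeks apart.

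**Month missing, last bottle never returned.** The dispensing month governs. Bottles hold 30 tablets (protocol 5.2.3). Dispensed 31 January 2019 and taken daily from that day, they last to 1 March. The rule gives 31 January, which is 29 days short.

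**Worked case (invented dates).** First dose 10 December 2018; true last dose 4 March 2019; bottles returned at early termination on 5 March; day of last dose not recorded.

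| | Last dose | Exposure | Last dose + 30 days |
|---|---|---|---|
| Truth | 4 Mar | 85 days, 12.1 weeks | 3 Apr |
| SAP rule | 31 Mar | 112 days, 16.0 weeks | 30 Apr |
| Capped at return | 5 Mar | 86 days, 12.3 weeks | 4 Apr |

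Under the SAP rule the last dose falls 26 days after the drug was returned.

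**Effect on an arm mean.** The split of the 9 subjects is not given. If an arm has 4 or 5 subjects, one 30-day excess moves its mean exposure by 30/4 = 7.5 or 30/5 = 6 days.

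**The case against.** The strongest reply is that this is a contingency rule that may never be used. Protocol 9.1.5 requires the end date of study drug in source records, and SAP 2.2 has queries resolved, or adjudicated as unresolvable, before unblinding. Nothing shows that any of the 9 subjects lacks a date. Exposure is summarised descriptively and is never a denominator for AE rates. Drug administration is listed by subject and AEs are listed with their treatment-emergent flag, so a reader could trace an odd case. All of this stands, and it limits the point to a minor one. It does not make the rule right.

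Four stronger readings are tempting, and the documents do not support them.

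- A reader might infer that the rule always overstates exposure. It does not: the unreturned-bottle case falls short.
- A reader might infer that events up to 60 days after the true last dose (30 + 30) will be counted as treatment-emergent. Protocol 7.3 requires AE reporting only to 30 days after last administration. The general definition in SAP 7.1.5.1 runs from permanent discontinuation of drug, and SAP 7.1.5.2 covers only incomplete onset dates. The real exposure to this risk is in subjects who stop drug but stay on visits, which protocol 3.5.2 allows.
- A reader might picture bottles routinely coming back at follow-up. Drug accountability is not scheduled at that visit, so this would be off schedule.
- A reader might assume that early drop-outs are the ones with missing dates. That is plausible, but neither document says so.

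**Conclusion.** Wrong as written, and minor. For an incomplete last-dose date, SAP 4.2.1 can give a last dose later than the return of the last bottle or the subject's exit. Death is the only written limit. Because it sits in the month-missing paragraph, it may not, read literally, reach the month-known case at all.

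With the month known, the excess is at most 30 days. The average of about 15 rests on evenly spread dates. With the month missing, the size depends on the return lag, and the error can go in either direction. The consequences fall mainly on reported exposure and, for subjects who stop drug but remain on visits, on the safety windows. The summary cut-off is partly protected because SAP 3.8.2 already keeps data to the follow-up visit when that is later. If all 9 subjects have complete last-dose dates, no result changes.

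**What to change.** In SAP 4.2.1, replace the death limit with one sentence covering both the month-known and month-missing cases. The imputed last dose is the earliest of (a) the date from the current month-end rule, (b) the return date of the last-dispensed bottle, (c) the early termination visit, (d) the study discontinuation or completion date, and (e) death. It is to be no earlier than the last dispensing date and, when the month is recorded, no earlier than the first day of that month.

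The words *last-dispensed* are essential. Bottles are accounted for throughout treatment, so a cap at the earliest return of any bottle would pick an early one and collapse the result to the last dispensing date, up to about four weeks short.

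The cost is one sentence and a small programming change, using dates the protocol already requires. The downside is slightly shorter reported exposure and a slightly narrower safety window for any affected subject. A cap cannot repair the unreturned-bottle shortfall, so the SAP should acknowledge that limit.

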4.2.2. Adherence to Study Drug

An adherence to study drug will not be summarized.

A by-subject listing of study drug administration will be provided by subject ID number (in ascending order) and visit (in chronological order).

4.3. Protocol Deviations

A by-subject listing will be provided for those subjects who did not meet at least 1 eligibility (inclusion or exclusion) criterion. The listing will present the eligibility criterion (or criteria if more than 1 deviation) that subjects did not meet and related comments, if collected.

Protocol deviations occurring after subjects entered the study are documented during routine monitoring. A by-subject listing will be provided for the subjects with important protocol deviation.

5. BASELINE CHARACTERISTICS

5.1. Demographics

Subject demographic variables (i.e., age, sex, race, and ethnicity) will be summarized by treatment group and overall using descriptive statistics for age, and using number and percentage of subjects for sex, race, and ethnicity. The summary of demographic data will be provided for the Safety Analysis Set. The summary of demographic data will include the following:

- Age (on the first dose date of any study drug) as a continuous variable
- Age group (< 50, \geq 50 years)
- Race
- Ethnicity (Hispanic or Latino, not Hispanic or Latino)
- Sex

A by-subject demographic listing, including the informed consent date, will be provided by subject ID number in ascending order.

5.2. Other Baseline Characteristics

The baseline characteristics include:

- Prior treatment with cyclophosphamide (Yes, No)
- 24-hour urine protein (< 3g/d, \geq 3g/d)
- Baseline 24-hour urine protein
- Baseline eGFR
- Baseline UPCR (average of 2 morning voids)
- UPCR from a 24-hour urine collection
- Current treatment with systemic corticosteroids (Yes, No)

The baseline characteristics will be summarized by treatment group and overall using descriptive statistics (n, mean, SD, median, Q1, Q3, minimum, and maximum) for continuous variables and using number and percentage for categorical variables.

The summary of baseline characteristics will be provided for the FAS. No formal statistical testing is planned.

A by-subject listing of other baseline characteristics will be provided by subject ID number in ascending order.

5.3. Medical History

Medical history will be listed.

6. EFFICACY ANALYSES

6.1. Primary Efficacy Endpoint

The primary endpoint is the percent change in urine protein from Baseline (Day 1) to Week 16. Urine protein is assessed by urinary protein excretion during a 24-hour urine collection.

6.1.1. Statistical Hypothesis for the Primary Efficacy Endpoint

No statistical hypotheses will be tested.

6.1.2. Analysis of the Primary Efficacy Endpoint

The primary endpoint, the percent change from Baseline (Day 1) in 24-hour proteinuria at Week 16 will be presented in descriptive statistics for each treatment group.

6.2. Secondary Efficacy Endpoints

6.2.1. Definitions of Key Secondary Efficacy Endpoints

The secondary efficacy endpoints include:

- Change from Baseline (Day 1) in urine protein (assessed by urine protein excretion during a 24-hour urine collection) at Week 16
- Change from Baseline (Day 1) in eGFR at Week 16
- Change from Baseline (Day 1) in UPCR (assessed by urine protein excretion during a 24-hour urine collection) at Week 16
- Proportion of subjects with partial remission (defined as urine protein excretion below < 3 g/d and urine protein excretion decrease by $\geq 50\%$ among subjects with Baseline (Day 1) nephrotic range proteinuria [urine protein excretion ≥ 3 g/d]; or urine protein excretion decrease by $\geq 50\%$ among subjects with subnephrotic range proteinuria [urine protein excretion < 3 g/d]) at Week 16
- Proportion of subjects with complete remission (defined as urine protein excretion below 0.5 g/day, with no hematuria) at Week 16

